# 2. LIST OF ABBREVIATIONS AND DEFINITION OF TERMS

AEs Adverse Events

ALT Alanine Transaminase
ANC Absolute Neutrophil Count
Anti-D Anti-D immunoglobulin
AST Aspartate Transaminase
AUC Area under the curve

AUC $_{(0-\tau)}$  Area under the plasma concentration-time curve of the dosing interval Area under the plasma concentration-time curve of the dosing interval

standardized to one week

BMI Body Mass Index

BPL Bio Products Laboratory Limited (Ltd.) (the Sponsor and manufacturer)

BUN Blood Urea Nitrogen
CBC Complete Blood Count
CI Confidence Interval
CL Systemic clearance (PK)

Cmax Maximum concentration in plasma
CFR Code of Federal Regulations
CRO Contract Research Organization

Cryo-Store Archive Facility for Laboratory Samples

CV Coefficient of Variation
DVT Deep Vein Thrombosis
eCRF Electronic Case Report Form
EMA European Medicines Agency

EU European Union

FDA U.S. Food & Drug Administration

HAV Hepatitis A Virus

HBsAg Hepatitis B Surface Antigen

HBV Hepatitis B Virus

HCG Human Chorionic Gonadotropin

HCV Hepatitis C Virus

HIV Human Immunodeficiency Virus

IB Investigator's Brochure

ICH International Conference on Harmonization

IEC Independent Ethics Committee

IgA Immunoglobulin A
IgG Immunoglobulin G

IGIV Immunoglobulin Intravenous

IgM Immunoglobulin M

IMP/IP Investigational Medicinal Product / Investigational Product (EU / US)

IRB Institutional Review Board ITT Intent-To-Treat (population)

IV Intravenous

LDH Lactate Dehydrogenase

Page 7 of 87

MOsmol MilliOsmolae mL Milliliter

NAT Nucleic acid Amplification Test (PCR)

PA Posterior-Anterior

PaO2 Partial pressure of Oxygen in arterial blood

PCR Polymerase Chain Reaction

PID Primary Immunodeficiency Diseases

PK Pharmacokinetic
PVC Polyvinyl Chloride
RNA Ribosenucleic Acid
SAE Serious Adverse Event

SC Subcutaneous SCIG Subcutaneous IgG

SOP Standard Operating Procedure

SUSAR Suspected Unexpected Serious Adverse Reaction

TEAE(s) Treatment-emergent Adverse Event(s)

TEE Thrombo-embolic events

tmax Time to reach the maximum concentration in plasma

UK United Kingdom US United States

#### 3. PROTOCOL SYNOPSIS

Name of Sponsor/Company: Bio Products Laboratory Ltd. (BPL) [name]	Name of Manufacturer: Bio Products Laboratory Ltd. (BPL) [name]	
Name of Finished Product:	Protocol identification code:	
Subgam  VF	SCIG03	
Name of Active Ingredient:	Protocol Synopsis version and date:	
Immune Globulin (Human)	Version 6, 22 March 2017	

Title of study: A Phase III, Multicenter, Open-Label Study to Evaluate the Pharmacokinetics and Safety of Subgam-VF in Primary Immunodeficiency Diseases (PID)

Indication: Primary immunodeficiency diseases

Study centers: This will be a multicenter study planned for the US, but depending upon the availability of suitable subjects may be extended into other countries.

Development phase: III

#### **Objectives:**

#### **Primary Objective**

• To determine the PK profile of Subgam-VF and compare the AUC(0-τ) with historical AUC data (all standardized to one week at steady state) from Gammaplex 5% IGIV PID studies (GMX01 and GMX04).

#### Secondary Objectives

- To assess the safety of Subgam-VF, including the incidence of adverse events and site infusion reactions in subjects with PID.
- To refine the dose adjustment coefficient for Subgam-VF

#### **Exploratory Objective**

• To explore PK modelling for alternative dosing schedules.

## Study design:

This will be a Phase III, multicenter, open-label, non-randomized study.

- Following a screening period, eligible subjects will commence weekly Subgam-VF treatment; this is a 16% subcutaneous IgG product.
- Subjects will receive Subgam-VF for 26 weeks during which time safety will be assessed.
- After Week 21, PK sampling will commence to measure AUC(0-τ).
- The patient populations will be as similar as possible to that of the historical studies (GMX01 and GMX04) as per similar inclusion/exclusion criteria.
- Comparable methods will be used to determine PK concentrations to that of the historical studies and the AUC measured will be at steady state.
- Follow-up visit (one week after the last Subgam-VF infusion, Week 27). All AEs will be monitored up to 28 days after the last Subgam-VF infusion by telephone contact (Week 30).
- The initial weekly dose of Subgam-VF administered will be calculated by taking the average weekly equivalent of the subject's IGIV dose (should be stable, as in same mg/kg +/- 5%), divided by the average dosing interval in weeks (i.e. 3 or 4), multiplied by 1.37, a dose adjustment coefficient based on other licensed subcutaneous IgG products. If the subject was already receiving a weekly SCIG IgG there will be no dose adjustment.
- Oral and parenteral steroids as concomitant medication are allowed if the average daily dose is < 0.15 mg of prednisone equivalent/kg body weight per day.

## Page 9 of 87

Name of Sponsor/Company: Bio Products Laboratory Ltd. (BPL) [name]	Name of Manufacturer: Bio Products Laboratory Ltd. (BPL) [name]	
Name of Finished Product:	Protocol identification code:	
Subgam VF	SCIG03	
Name of Active Ingredient:	Protocol Synopsis version and date:	
Immune Globulin (Human)	Version 6, 22 March 2017	

- Routine premedication to reduce potential adverse effects associated with SCIG infusions are discouraged. Exceptions;
  - Premedication will be permitted if a subject has reported systemic adverse events on two Subgam-VF infusions.
  - Local anesthetics (e.g. an analgesic cream) can be used before Subgam-VF infusion to reduce the potential pain associated with needle insertion if required.
- Subgam-VF will be administered subcutaneously using infusion pumps.
- Subjects will be given diaries to record adverse event data as well as any infusions administered at home. In addition there will be a telephone follow up by an appropriately qualified site staff member on day 3 after each site administered and home administered infusion to check for any adverse reactions including infusion site reactions and remind subjects to document these in their subject study diary. The date of infusion is considered to be Day 0. If Day 3 is to fall on a weekend or public holiday then this telephone follow up call should be performed on the closest working day after Day 3 as possible.

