# Test product, dose/mode of administration, batch number(s)

Subgam-VF is a 16% IgG and will be administered weekly, by subcutaneous infusion:

• The initial weekly dose of Subgam-VF administered will be calculated by taking the average weekly equivalent of

Page 14 of 87

Name of Sponsor/Company:	Name of Manufacturer:
Bio Products Laboratory Ltd. (BPL)	Bio Products Laboratory Ltd. (BPL)
[name]	[name]	[name]
Name of Finished Product:	Protocol identification code:
Subgam  VF	SCIG03
Name of Active Ingredient:	Protocol Synopsis version and date:
Immune Globulin (Human)	Version 6, 22 March 2017

the subject's IGIV dose (should be stable, as in same mg/kg +/- 5%), multiplied by 1.37, a dose adjustment coefficient based on other licensed subcutaneous IgG products. If the subject was already receiving a weekly SCIG IgG there will be no dose adjustment.

It is planned to use one batch of Subgam-VF in this study. Additional batches may be used if required. The following infusion rates will be followed.

Subgam-VF infusions will be administered in accordance with the table below:

Table 1 Volume and Rate of Subgam-VF infusions

1 + Orame una riure or Susgum + 1 imiusions		
	Volume	Rate
First infusion	20 mL/site	20 mL/hr/site
Maximum at	Up to 30 mL/site	Up to 30 mL/hr/site
subsequent		
infusions		

- Up to 6 infusion sites can be used simultaneously. Subjects weighing ≥100 kg may use up to 8 sites if necessary. If more sites are required, these must be used consecutively (during the same infusion).
- Any increase in flow rate or number of sites should first be tried whilst the subject is in the clinic. However, the infusions must be administered at the volume and rate outlined in Table 1 throughout the entire infusion. **Titration during the infusion is not allowed.**
- For young children or adults of below average weight, lower flow rates may be used, depending on tolerability.

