## 7. STUDY DESIGN AND PLAN

This will be a Phase III, multicenter, open-label, non-randomized study. Up to 50 subjects will be enrolled to ensure 30 evaluable subjects. At least 18 subjects will be adults (aged 16-75 years) and 12 will be children split between the age groups 2 to 5 years (i.e. not reached their 6th birthday), 6 to 11 years (i.e. not reached their 12th birthday) and 12 to 15 years (i.e. not reached their 16th birthday), with a minimum of 4 in each age group.

All children who receive at least one infusion of Subgam-VF will be included in the safety analysis. Due to the potential for early withdrawals, PK data may not be available on all 12 children and there may be fewer than 12 evaluable children in the PK analysis. The total number of subjects (adults plus children) evaluable for PK analysis will be at least 30.

Subjects will receive 26 infusions (weeks) of Subgam-VF at a weekly dose equivalent to 1.37 of their IGIV dose (expressed as mg/kg/week). If the subject was already receiving a weekly SCIG IgG there will be no dose adjustment. Pharmacokinetics and safety of Subgam-VF will be assessed.

All subjects will undergo a pharmacokinetic (PK) profile after the 21st infusion of Subgam-VF (see PK Assessment Schedule, Table 3). Where an appropriately qualified member of the study team is available, arrangements will be made to collect the PK samples from Steady State Day 1 (24 hours post-infusion) onwards at the subject's home to reduce the number of visits to the sites. Alternatively a Home Health Agency may be utilized to take the PK samples outside of the investigational site. The subject would be required to sign an extra IRB/EC approved consent form to permit the site to share the subject's details with the agency in order for them to collect the sample.

In the case of younger children it is important not to exceed the maximum blood withdrawal volumes stated in Appendix V. Therefore smaller volumes of blood will be taken. See the Laboratory Manual for details.

- Following a screening period, eligible subjects will commence weekly Subgam-VF treatment; this is a 16% subcutaneous IgG product.
- Subjects will receive Subgam-VF for 26 weeks during which time safety will be assessed

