 The definition of an adult as  $\geq$  16 years is as per the FDA guidance for PK studies. Note this does not affect the requirements for consent/assent, for which each site should follow their IRB guidelines.

- After Week 21, PK sampling will commence to measure  $AUC_{(0-\tau)}$  over 7 days.
- The patient populations will be as similar as possible to that of the historical studies (GMX01 and GMX04) as per similar inclusion/exclusion criteria.
- Comparable methods will be used to determine PK concentrations to that of the historical studies and the AUC measured will be at steady state.
- Follow-up visit Week 27 (one week after the last Subgam-VF infusion).
- Follow-up telephone call Week 30 (four weeks after the last Subgam-VF infusion).
- The initial weekly dose of Subgam-VF administered will be calculated by taking the average weekly equivalent of the subject's IGIV dose (should be stable, as in same mg/kg +/- 5%), multiplied by 1.37, a dose adjustment coefficient based on historical data for other subcutaneous IgG products. If the subject was already receiving a weekly SCIG IgG there will be no dose adjustment.
- Oral and parenteral steroids as concomitant medication are allowed if the average daily dose is < 0.15 mg prednisone equivalent/kg body weight per day. Short or intermittent courses of > 0.15 mg/kg/day are allowed if required.
- Routine premedication to reduce potential adverse effects associated with SCIG infusion are discouraged. Exceptions:
  - Premedication will be permitted if a subject has reported systemic adverse events on two Subgam-VF infusions.
  - Local anesthetics (e.g. an analgesic cream) can be used before any Subgam-VF infusion to reduce the potential pain associated with needle insertion if required.
- Subgam-VF will be administered subcutaneously using infusion pumps.
- Subjects will be given diaries to record adverse event data as well as any infusions administered at home.

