# 8.2. Investigational Treatment

# 8.2.1. Dosing Schedule and Rationale

Subgam-VF is a 16% subcutaneous IgG product. The weekly dose of Subgam-VF administered will be calculated by taking the weekly equivalent of the subject's stable IGIV dose, multiplied by 1.37, a dose adjustment coefficient based on other licensed subcutaneous IgG products. If the subject was already receiving a weekly SCIG IgG there will be no dose adjustment. The Subgam-VF dose should remain the same throughout the study, if a subject's weight changes by >5% compared with baseline (screening) or the previous visit, the dose should be adjusted accordingly with the aim of maintaining a stable dose in terms of mg/kg. If the dosage needs to be increased to achieve the required trough IgG level, then this should first be discussed with the CRO Medical Monitor, who will, if needed, discuss with the Sponsor.

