## 13.6.1. Primary Statistical Analysis

Data will be pooled with historical data and a treatment variable defined (Subgam-VF or Gammaplex IGIV). Log transformed  $sAUC_{(0-\tau)}$ , ( $AUC_{(0-\tau)}$  standardized to one week) will be analyzed using a mixed model fitted including treatment, and allowing for variability to be different between treatment groups. The mean difference (Subgam-VF or Gammaplex IGIV) between treatments with 90% Confidence Interval (CI) will be back transformed to give an estimate of the ratio (Subgam-VF/ Gammaplex IGIV) of  $sAUC_{(0-\tau)}$ . If the resulting 90% CI for the ratio lies within the equivalence limit of (0.80, 1.25), it will be concluded that there is equivalence in  $sAUC_{(0-\tau)}$  and thus the dosing factor of 1.37 for Subgam-VF (in addition to the adjustment for dosing interval) gives equivalent exposure at steady state to Gammaplex IGIV.

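### The synopsis divides an already weekly IGIV dose by the 3- or 4-week interval a second time, which contradicts every other statement of the dose rule by a factor of 3 or 4

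*Protocol*

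**What the plan says.** The rule for converting a subject's IGIV dose to the weekly Subgam-VF dose appears in several places in the current protocol (version 6) and once in the SAP.

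- Synopsis, Study design: the dose is "calculated by taking the average weekly equivalent of the subject's IGIV dose (should be stable, as in same mg/kg +/- 5"%), and the sentence continues "divided by the average dosing interval in weeks (i.e. 3 or 4), multiplied by 1.37".
- Synopsis, Test product: the weekly equivalent of "the subject's IGIV dose (should be stable, as in same mg/kg +/- 5%), multiplied by 1.37, a dose adjustment coefficient". There is no division.
- Section 7, third paragraph: a "weekly dose equivalent to 1.37 of their IGIV dose (expressed as mg/kg/week"). SAP section 5.1 repeats this statement.
- Section 7, bullet on the initial dose: "taking the average weekly equivalent of the subject's IGIV dose (should be stable, as in same mg/kg +/- 5%), multiplied by 1.37". There is no division.
- Section 8.2.1: "calculated by taking the weekly equivalent of the subject's stable IGIV dose, multiplied by 1.37". There is no division.
- Section 13.6.1, repeated in the synopsis: the equivalence conclusion concerns "the dosing factor of 1.37 for Subgam-VF (in addition to the adjustment for dosing interval"), which describes one interval adjustment plus the factor.

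Subjects already on weekly SCIG receive no adjustment, so the point concerns only subjects coming from IGIV.

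**The concern.** The synopsis bullet starts from a quantity that is already per week and divides it by the number of weeks again. Followed word for word, it gives a third or a quarter of the dose obtained from the other statements. This is operative text, not an amendment log.

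Two things are at stake. The first is each affected subject's IgG replacement, because two sites reading different pages could start comparable subjects on very different doses.

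The second is what the trial can conclude. The primary analysis, if equivalence is shown, attributes it to the factor 1.37. The refined coefficient in section 13.6.2 is 1.37 divided by the exposure ratio. It is always estimated in the PK Dose-Adjustment population, whose Subgam-VF members all came from IGIV (section 13.2.2.3), and these are the subjects the contradiction affects. If any of them were dosed by the synopsis bullet, 1.37 would not be the factor they received.

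**Working it through.** **Inputs.** The intervals are 21 or 28 days, so k = 3 or 4 weeks (section 6.1, criterion 4c). Eligible IGIV doses are 300 to 800 mg/kg/month and eligible SCIG doses 110 to 300 mg/kg/week (criterion 4a). The factor is 1.37. The 400 mg/kg infusion used below is an illustration, not a figure from the plan.

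**Formulas.** Let D be the dose per infusion and W = D/k the weekly equivalent.

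- Test product paragraph, section 7 bullet and section 8.2.1: dose = 1.37 × W.
- Synopsis study design bullet, as written: dose = 1.37 × W/k.

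**The plan's own figure.** Section 7 and SAP section 5.1 state the multiplier on the weekly IGIV dose as 1.37. The first formula reproduces it for both intervals. The second gives 1.37/3 = 0.457 or 1.37/4 = 0.3425 and does not reproduce it.

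**Examples.**

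| IGIV regimen | W (mg/kg/week) | 1.37 × W | 1.37 × W/k | Ratio |
|---|---|---|---|---|
| 400 mg/kg every 28 days | 400/4 = 100 | 137.0 | 34.25 | 4 |
| 400 mg/kg every 21 days | 400/3 = 133.3 | 182.7 | 60.9 | 3 |

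The ratio is exactly k, whatever the dose.

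**Across the eligible range.** The plan does not define a month, so both readings are shown.

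| Month taken as | W | 1.37 × W | 1.37 × W/3 | 1.37 × W/4 |
|---|---|---|---|---|
| 4 weeks | 75 to 200 | 102.75 to 274 | 34.25 to 91.3 | 25.7 to 68.5 |
| Calendar month (12/52.18) | 69.0 to 184.0 | 94.5 to 252 | 31.5 to 84.0 | 23.6 to 63.0 |

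Under either definition, every dose from the synopsis bullet lies below the protocol's own SCIG entry range of 110 to 300 mg/kg/week. Doses from the other formula mostly fall inside it, starting slightly below its lower end.

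**Variant.** If the base in the synopsis bullet were the per-infusion dose D, then 1.37 × D/k = 1.37 × W and the statements would agree. The bullet, however, names the weekly equivalent as its base.

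**The case against.** The strongest reply is that this is a drafting slip in one bullet. The division can be read as explaining how the weekly equivalent is obtained, and on that reading no discrepancy exists. The other statements all point the same way, including the synopsis's own test product paragraph and the section devoted to dosing. The literal reading also looks odd on its face: it lowers the weekly dose although the coefficient exceeds 1, and its results fall below the SCIG entry range. Troughs are measured from screening onwards at clinic visits, section 7.12 gives a minimum target trough of 600 mg/dL, and SAP section 13.1 computes the actual mg/kg at each infusion, so a three- or fourfold departure would be visible. Nothing in the documents shows that any site dosed this way.

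Much of this stands. The benign reading is plausible, and no misdosing is claimed. But that reading requires setting aside the words of the sentence, and no statement gives the body of the protocol precedence over the synopsis. Trough and dose checks would reveal a misapplied rule only after subjects had been dosed. Section 8.2.1 also intends the dose to stay constant in mg/kg, and a later increase to reach the required trough would break that.

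**Conclusion.** The contradiction is real in the current text. For every subject coming from IGIV, the synopsis study design bullet taken literally and the other statements of the rule differ by exactly 3 (21-day interval) or exactly 4 (28-day interval). That result is exact and depends only on reading the bullet as written. The mg/kg ranges also depend on how a month is defined, but both definitions tried lead to the same conclusion. The practical effect is nil if all sites used the same formula and that formula applied 1.37 to the weekly dose; the documents do not show whether they did. Because this is the rule that sets the study dose and underlies both the primary conclusion and the refined coefficient, it must be corrected. No view is taken here on which dose rule is clinically appropriate.

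**What to change.** Reconcile the synopsis (Study design and Test product), section 7, section 8.2.1 and SAP section 5.1 to one written formula that names its base quantity (per infusion or per week) and shows the interval adjustment once, explicitly. One worked example for a 21-day subject and one for a 28-day subject would remove any remaining doubt; they are helpful but not essential. The sponsor should decide and state which formula was intended.

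Before the PK analysis, it would also be sensible to compare each IGIV-prior subject's actual first dose in mg/kg with the recorded prior dose and interval, and so confirm which factor was applied. Section 7.12 already requires the prior dose and interval to be recorded, and SAP section 13.1 already derives the actual dose.

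The cost is a short text correction in the next protocol version and, if the comparison is made, one listing from existing data. Data collection does not change.

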#### Screening/Baseline

After informed consent/assent (as appropriate):

Screening/baseline – subjects receive their usual dose of IGIV/SCIG and have all safety screening tests performed, including biochemistry, hematology, virology, vital signs and serum IgG trough levels.

#### **Treatment Period (Weeks 1 to 26)**

Eligible subjects return 7 days (+/- 1 day) after the Screening/Baseline visit for their first Subgam-VF dose (Week 1 visit). Weekly dosing with Subgam-VF will be administered for 26 weeks during which time safety will be assessed.

Week 21 to Week 22: Subjects will undergo PK sampling between two treatment visits to measure  $AUC_{(0-\tau)}$  (sample taken pre dose, then at 1, 2, 3, 5 and 7 days post dose, defined as Steady State Day 0, Steady State Day 1, Steady State Day 2, Steady State Day 3, Steady State Day 5, Steady State Day 7). If the PK sampling cannot be completed at Week 21 (eg. due to patients work/vacation schedule) then this can be delayed to start at Week 22, 23, 24 or 25; however, the patient should still visit the office/hospital for their week 21 infusion and complete the other assessments scheduled for Visit 8, if possible. Week 22 assessments (Visit 9) will normally coincide with the PK sampling Day 7. However, if PK sampling is delayed, Visit 9 will also be delayed.

If the subject is not already receiving IgG via the subcutaneous route, it is planned that home infusion will begin on Week 3 (3rd infusion of Subgam-VF), following training by the site during the preceding Subgam-VF visits. However, if the subject requires further assistance this will be provided (i.e. it is not mandatory that the infusions are performed at home).

The subject will return to the clinic every four weeks for a safety assessment (haematology, chemistry, pre and post dose vital signs and physical exam). Their regular Subgam-VF infusion will be given whilst the subject is at the clinic and additional Subgam-VF vials will be dispensed. Trough levels will also be measured at the clinic visits.

# Follow-up visit

Final safety assessments will be carried out approximately seven days after the final study infusion. All AEs will be monitored up to 28 days after the last Subgam-VF infusion by telephone contact.

Page 10 of 87

Name of Sponsor/Company:	Name of Manufacturer:	
Bio Products Laboratory Ltd. (BPL)	Bio Products Laboratory Ltd. (BPL)	
[name]	[name]	[name]	
Name of Finished Product:	Protocol identification code:	
Subgam  VF	SCIG03	
Name of Active Ingredient:	Protocol Synopsis version and date:	
Immune Globulin (Human)	Version 6, 22 March 2017	

